5.2.2 Clinical Studies

Two (2) Phase 1 studies in healthy adult subjects (ME3183-1 and ME3183-2 studies) have been conducted and 126 individuals who received study treatment (96 subjects received ME3183 and 30 subjects received placebo). ME3183 was tolerable and safe in healthy adults up to 25 mg single administration, and 10 mg twice daily (BID) and 15 mg QD for 14 days multiple administrations. Frequently reported treatment-emergent adverse events (TEAEs), the TEAEs reported by more than 2 subjects, in single administration were diarrhea, headache, lipase increased, tachycardia, and nausea. The majority of TEAEs in single ascending dose (SAD) studies were classified as mild. Most of the TEAEs were recovered/resolved within few days without any medication. The serious adverse event (SAE) of severe vasovagal neurocardiac syncope occurred in 12.5 mg subject. When ME3183 were administered repeatedly, the frequently reported TEAEs were; medical device site reaction, headache, diarrhea, abdominal pain, vomiting, nausea, hematochezia, back pain, arthralgia, pain in extremity, myalgia, dermatitis, decreased appetite, and dysmenorrhea. The majority of TEAEs in multiple ascending dose (MAD) study were classified as mild. All TEAEs were temporal and resolved during the dosing period. No SAE was occurred in MAD study.

ME3183 was administered to healthy adult subjects in either in suspension (1 mg to 12.5 mg) or capsule (12.5 mg to 25 mg) in SAD studies. ME3183 was absorbed orally in both form with peak concentration recorded at approximately 3.5 hours to 4 hours postdose and was eliminated slowly with an elimination half-life ($t_{1/2}$) of approximately 16 hours to 24 hours. The means of C_{max} and AUC increased slightly greater than a dose proportionality from 1 mg to 10 mg suspension, while C_{max} and AUC increased almost dose proportionally over the dose range of 12.5 mg to 25 mg of capsule administration. The means of C_{max} and AUC in CCI [REDACTED] (metabolite of ME3183) were approximately from [REDACTED] % to [REDACTED] % compared with those of ME3183 at each dose level. As the dose of ME3183 increases, the ratio of C_{max} and AUC of CCI [REDACTED] to ME3183 tended to decrease. The mean of cumulative urinary excretion rate in ME3183 was [REDACTED] % to [REDACTED] % which was quite small.

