7.2 Discussion of Study Design

A double-blind, randomized, placebo-controlled study is considered a gold-standard for conducting any interventional study. This design will minimize bias and provide reference data (ie, data from placebo treatment group) for comparison of the efficacy and safety parameters of the ME3183.

Psoriasis is a chronic immune-mediated inflammatory disorder, which requires a chronic therapy. Primary efficacy assessments of psoriasis clinical studies are usually performed at 12 or 16 weeks after initiation of study treatment. This is therefore considered an acceptable treatment duration to observe a CS response that allows for discriminating among different tested doses of ME3183. Primary evaluations of apremilast, the only PDE4 inhibitor currently approved for psoriasis treatment, were also conducted at week 16. A 16-week Treatment Period was also deemed acceptable for the placebo arm because psoriasis is not a life-threatening disease; in case of unbearable flares, subjects can discontinue early from the study and receive appropriate treatment.

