7.4 Early Termination

If a subject withdraws or is terminated from study treatment prior to completion of all study periods, all data collected at Visit 8 (Day 113) should be collected at the time of early termination. The subject will be asked to return to the study site 4 weeks after the last dose of study drug to complete the follow-up visit assessments (those performed on Day 141) as indicated in the Schedule of Assessments ([Table 1](#)).

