	Screening (Visit 1)	Visit 2	Visit 3	Visit 4	Visit 5	Visit 6	Visit 7	Visit 8 ^a	Follow-up Visit (Visit 9)
	Week -4	Week 0	Week 1	Week 2	Week 4	Week 8	Week 12	Week 16	Week 20
	Days -28 to -1	Day 1 (Baseline)	Day 8 (± 1 day)	Day 15 (± 1 day)	Day 29 (± 3 days)	Day 57 (± 3 days)	Day 85 (± 3 days)	Day 113* (± 3 days)	Day 141** (± 3 days)
Subject to return back unused study treatment for compliance check	-	-	X	X	X	X	X	X	-
Schedule the date/time for the next visit	X	X	X	X	X	X	X	X	-
Discharge the subject from the study site ^c	X	X	X	X	X	X	X	X	X

Abbreviations: β -hCG = β -human chorionic gonadotropin; AE = adverse event; BMI = body mass index; BSA = body surface area; C-SSRS = Columbia-Suicide Severity Rating Scale; DLQI = Dermatology Life Quality Index; ECG = electrocardiogram; FSH = follicle-stimulating hormone; HBV = hepatitis B virus; HCV = hepatitis C virus; PASI = Psoriasis Area and Severity Index; **CCl** ; PK = pharmacokinetic; PRO = patient-reported outcome; QTcF = QT interval corrected using Fridericia's formula; SAE = serious adverse event; sPGA = Static Physicians Global Assessment; WOCBP = women of childbearing potential; NRS = numerical rating scale.

* The duration of the Treatment Period is from Day 1 to Day 112 and the end of Treatment Period assessments will be performed on Day 113.

** The duration of the Follow-up Period is from Day 114 to Day 141 and the end of Follow-up Period assessments will be performed on Day 141.

^a or Early Termination Visit.

^b Subjects who discontinued or withdrew early from study treatment should return after 4 weeks of last dose of study treatment for follow-up safety assessments.

^c Must include history of drug, substance, or alcohol abuse/dependence within 1 year prior to Screening as determined by the investigator.

^d Record height at Screening only.

^e 12-lead ECG must include QTcF measurement.

^f All subjects must have the following viral serology tests completed at Screening: anti-HCV antibody, HBV surface antigen, HBV core antibody, HIV-1 antibody, and HIV-2 antibody. If the subject tests positive for anti-HCV antibody, then HCV RNA via polymerase chain reaction should be performed to confirm or rule out active infection. If the subject has received documented treatment which was curative for HCV and tests negative for HCV ribonucleic acid (RNA) at Screening, the subject may be considered for enrollment.

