### 7.2. Estimands for Secondary Efficacy Endpoints

The estimands for secondary efficacy endpoints are defined as below:

- Population: Subjects with moderate to severe plaque psoriasis defined by the study inclusion/exclusion criteria in [Section 4.2](#). The analysis population for the secondary efficacy endpoints will be full analysis set as defined in [Section 6.2](#).
- Variables:
  - Continuous variables measuring the percent changes from baseline in PASI score at all visits from Week 1 to Week 16
  - Binary variables indicating whether the subject has achieved  $\geq 50\%$ ,  $75\%$ ,  $90\%$  and  $100\%$  reduction from baseline in the PASI score at all visits from Week 1 to Week 16
  - Time to event variable measuring the time from baseline to the time achieving  $\geq 50\%$  and  $75\%$  reduction in PASI score in days respectively, censored by the date of last PASI assessment date for subjects who never achieves  $\geq 50\%$  or  $75\%$  reduction
  - Binary variables indicating whether the subject has achieved a sPGA score of "0" ("clear") or "1" ("almost clear") combined with a 2-point reduction on the 5-point sPGA scale at all visits from Week 1 and Week 16
  - Continuous variables measuring the changes from baseline in BSA at all visits from Week 1 to Week 16
  - Continuous variables measuring the changes from baseline in NRS at all visits from Week 1 to Week 16
  - Continuous variables measuring the changes from baseline in DLQI score at all visits from Week 1 to Week 16

This document is confidential.

- Binary variables indicating whether a subject achieves at least a 5-point reduction from baseline in the DLQI score at all visits from Week 1 to Week 16
- Population-level summary:
  - Binary variables will be summarized using numbers and proportions of subjects achieving that outcome of interest, then differences in the proportions between each ME3183 treatment group and placebo group will be calculated.
  - Continuous variables will be summarized using descriptive statistics by treatment group and overall. Mixed-effect model for repeated measures will be used to estimate the least-square (LS) mean differences between each ME3183 treatment group and placebo group.
  - Time to event variables will be summarized using medians and 95% CIs, Kaplan-Meier estimates, and hazard ratios estimated Cox proportional hazard models.
- Intercurrent events:

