  - Withdrawals or early terminations will be handled via while-on-treatment policy, where no missing data will be imputed, except for analyses listed below where intercurrent events will be handled via hypothetical strategy and missing data will be imputed using LOCF and NRI methods in addition to complete case analysis: percent change from baseline for PASI scores at all visits from Week 1 to Week 16, the numbers and percentages of subjects achieving  $\geq 50\%$ , 75%, 90% and 100% reduction from baseline in the PASI score at all visits from Week 1 to Week 16, the numbers and percentages of subjects achieving an sPGA score of "0" ("clear") or "1" ("almost clear") and a 2-point reduction from baseline.

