Descriptive statistics for the continuous secondary endpoints described above will be provided at each schedule visit by treatment group. Additionally, the secondary continuous efficacy endpoints (including percent changes for PASI, changes for DLQI, BSA and NRS) will be analyzed using a mixed-effect model for repeated measures (MMRM) with the change or percent change from baseline as the response variable, treatment group, visit, treatment-by-visit interaction as fixed effects, and the baseline value as a covariate. An unstructured covariance matrix will be used to model the correlation among repeated measurements. The Kenward-Roger adjustment will be used with restricted maximum likelihood (REML) to make proper statistical inference. The LS mean differences between ME3183 treatment groups and placebo at each scheduled visits along with the 2-sided 95% CIs and 2-sided p-values will be estimated from the MMRM model. In the event that MMRM with unstructured covariance matrix fails to converge, alternative covariance structures will be explored, including Toeplitz, heterogeneous Toeplitz, variance components, compound symmetry, heterogeneous compound symmetry, autoregressive and heterogeneous autoregressive covariance matrices, where the optimal covariance matrix structure will be selected based on Akaike's Information Criteria (AIC), where smaller values of AIC indicate better overall fit. MMRMs will be estimated for the secondary continuous efficacy endpoints using complete case analysis only.

Kaplan-Meier method will be used for summarizing the time to the first response of PASI-50 and PASI-75 in days. The time to the first response of PASI-50 and PASI-75 is defined as the number of days from the first dose of the study drug to the first response. If a subject does not achieve PASI-50 and PASI-75, the variable will be censored on the last PASI assessment date. Median time to response and 95% CI will be provided, when estimable. The CI will be based on log-log transformation. The reverse Kaplan-Meier plots of PASI-50 and PASI-75 will be presented by treatment group. The comparison of the time to PASI-50 and PASI-75 between each ME3183 treatment group and placebo will be performed using the log-rank test.

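### Time to PASI-50 and PASI-75 has no Week 16 or end-of-treatment limit, so for early terminators the censoring rule contradicts the SAP's own while-on-treatment strategy

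*SAP*

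**What the plan says.** SAP 10.2 measures time to PASI-50 and PASI-75 as "the number of days from the first dose of the study drug to the first response". For everyone else it says: "If a subject does not achieve PASI-50 and PASI-75, the variable will be censored on the last PASI assessment date". The variable definition in SAP 7.2 matches, with time "censored by the date of last PASI assessment date for subjects who never achieves" the required reduction. Neither section names a last eligible visit. In the endpoint lists (Protocol 6.2.2.2, SAP 5.2) every other secondary efficacy endpoint is confined to Week 1 to Week 16; the time-to-response line has no range.

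On intercurrent events SAP 7.2 states: "Withdrawals or early terminations will be handled via while-on-treatment policy, where no missing data will be imputed". It then lists exceptions: percent change in PASI, the PASI responder proportions and the sPGA responder proportion. Time to PASI-50 and PASI-75 is not among them.

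PASI is scored after dosing ends. The last dose is on Day 112, and Table 1 in both documents marks PASI at the follow-up visit (Week 20, Day 141). Subjects who stop early have the Visit 8 assessments at early termination. Protocol 7.4 then asks them back four weeks after the last dose to "complete the follow-up visit assessments (those performed on Day 141) as indicated in the Schedule of Assessments". Footnote b to Table 1 describes that return more narrowly: "Subjects who discontinued or withdrew early from study treatment should return after 4 weeks of last dose of study treatment for follow-up safety assessments".

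**The concern.** With no limit, the first PASI score that meets the threshold is the event, whenever it is seen, including about four weeks after the last dose. Protocol 7.2 also says that "in case of unbearable flares, subjects can discontinue early from the study and receive appropriate treatment", so some early stoppers could be on other therapy by then. Such a response would be credited to the randomized arm in the Kaplan-Meier medians, log-rank tests and Cox hazard ratios that SAP 10.2 commits to.

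The text also supports two derivations. One programmer could follow the censoring sentence in SAP 10.2 as written. Another could infer a cut-off from the estimand in SAP 7.2. If the choice were made after unblinding, it could be driven by the results.

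**Working it through.** The plan gives no event count, hazard ratio or power for this endpoint, so there is no figure to reproduce.

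**1. Is the follow-up visit off drug?** Protocol 5.2.2 gives a half-life of "approximately 16 hours to 24 hours". Four weeks is 28 × 24 = 672 hours. 672/24 = 28 and 672/16 = 42 half-lives. The visit is off drug.

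**2. Who is affected, and where on the time axis?**

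- *Early terminators.* A last dose on Day d puts the follow-up visit at about Day d + 28, which is before Day 113 whenever d < 85. Stopping at Day 29 or Day 57 gives follow-up at about Day 57 or Day 85, inside the main Kaplan-Meier window. SAP 7.2 calls for on-treatment data only, while the SAP 10.2 rule takes the follow-up score as an event or as the censoring date. These conflict.
- *Completers.* The last dose is on Day 112 and follow-up is on Day 141. An event or censoring at Day 141 cannot change Kaplan-Meier estimates up to Day 113. Planned end of dosing is neither a withdrawal nor an early termination, so the strategy in SAP 7.2 is not breached. The log-rank test, the Cox hazard ratio and any median reached after Week 16 can still move.

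**3. How many subjects?** The assumed 10% drop-out (Protocol 15.1, SAP 4.3) gives 0.10 × 125 = 12.5 early stoppers, or 12.5/5 = 2.5 per arm. Each extra response adds 1/25 = 4 points to an arm's crude response.

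**4. Illustration with assumed counts.** Each arm has 25 subjects and 3 non-responding early terminators (last visit Day 57, follow-up Day 85). First PASI-75 responses by Week 16 are 9 on active (1, 2, 3 and 3 at Days 29, 57, 85 and 113) and 3 on placebo (1 each at Days 57, 85 and 113). The analysis is a Cox model with Efron ties and a two-sided log-rank test.

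| Rule and follow-up responses | Hazard ratio | p |
|---|---|---|
| Limited to Week 16 or early termination | 3.51 | 0.045 |
| No limit, none | 3.49 | 0.046 |
| No limit, 1 extra on placebo | 2.60 to 2.66 | 0.093 to 0.099 |
| No limit, 2 extra on placebo | 2.05 to 2.15 | 0.16 to 0.18 |
| No limit, 2 extra on active | 4.37 to 4.44 | 0.012 to 0.013 |

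Ranges depend on whether the extra events fall in completers or early terminators. The counts start close to 0.05, so a single event shows clearly.

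**5. How often might such events occur?** A simulation used 10,000 runs per scenario and 25 per arm, with assumed PASI-75 by Week 16 of 10% on placebo and 35% on active. Non-responders stop for flare at Week 4, 8 or 12, and all are treated and scored 28 days later. Completers' Week 20 responses are not modeled.

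| Flare stops, placebo/active | Stoppers reaching PASI-75 at follow-up | Mean extra events | Log-rank power, limited to unlimited |
|---|---|---|---|
| 5%/2% | 0% | 0 | 57.4% to 58.1% |
| 5%/2% | 10% | 0.18 (none in 84% of runs) | 57.3% to 56.2% |
| 4%/4% | 25% | 0.50 | 58.2% to 57.3% |
| 10%/4% | 25% | 0.88 | 56.4% to 50.3% |
| 10%/4% | 50% | 1.74 | 56.0% to 43.6% |
| 2%/8% | 50% | 1.27 | 60.1% to 65.0% |

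All response, stopping and rescue rates here are assumptions; none comes from the documents.

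**The case against.** The strongest reply is that SAP 7.2 already governs early stoppers. While-on-treatment applies, this endpoint is not an exception, and a programmer reading both sections has grounds to drop off-treatment scores. The mock shells (SAP 21) are in a separate document and may contain a cut-off. This supports a low severity. It does not remove the conflict, because the only operative censoring date in either section is the last PASI assessment.

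SAP 2.2 calls Visit 8 the final study visit, but it sets the timing of the analysis and not a data limit, and an early stopper's follow-up can come before Week 16 anyway. SAP 8.4 keeps visits as recorded. It is a windowing rule that neither includes nor excludes follow-up data.

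Three stronger readings might be inferred, and the documents do not support them:

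- *The rule breaches the estimand for every subject.* It does not, because the strategy covers withdrawals and early terminations, not planned end of dosing.
- *Responses on rescue therapy will routinely be counted.* Protocol Appendix 2 prohibits the main psoriasis therapies until four weeks after the last dose, which reaches the follow-up visit. Protocol 7.2 speaks of flaring subjects leaving the study, and footnote b leaves it unclear whether PASI is always taken in early stoppers. The route is open but narrow.
- *About 12 points of log-rank power are at risk.* That scenario needs placebo flare stops equal to the whole assumed drop-out, all treated and all scored, with half of earlier non-responders reaching PASI-75 in about four weeks. Nothing in the documents supports those rates.

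**Conclusion.** The point holds with a limited scope. The rule is wrong as written for early terminators, because the censoring rule conflicts with the estimand stated in the same SAP. For completers it is an unstated limit, inconsistent with the range of the other endpoints.

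The severity is minor. The endpoint is secondary in a proof-of-concept study with no formal sample size. The complete-case and non-responder-imputation analyses of the Week 16 primary endpoint are not touched; the LOCF version was not assessed. At about 2.5 early stoppers per arm, few off-drug first responses are likely, so the effect is probably small. One or two could still shift a hazard ratio or p-value at this sample size. The direction depends on which arm has more of them, which the documents do not give, and the size rests wholly on assumed rates.

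**What to change.** Before unblinding, add to SAP 10.2 and to the time-to-event variable in SAP 7.2: *Only PASI assessments up to and including the Week 16 or early termination visit are used; subjects without a response are censored at the last such assessment.*

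This is one statement in two places. It needs no new visits or data, it carries out the while-on-treatment strategy for early terminators, and it matches the Week 1 to Week 16 range of the other secondary efficacy endpoints. The small downside is that responses first seen at the follow-up visit no longer count as events.

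Censoring at the start of prohibited therapy should not be added in the same change. It would bring in a new intercurrent-event strategy, also for subjects still on study drug, when SAP 7.2 names only withdrawals and early terminations for the secondary efficacy endpoints.

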### 10.3. Exploratory Efficacy Endpoints and Analyses

CCI

This document is confidential.

## 11. Pharmacokinetics

The PK analysis set will be used for the PK analysis.

### 11.1. PK Sampling Schedule

Blood samples for quantitation of ME3183 and its metabolite (CCI [REDACTED]) will be collected at the time points indicated in Section 4.6 [Table 1](#) Schedule of Assessment. The actual date and time of each blood sample collection will be recorded in the subject's eCRF and will be reported in the PK listing. The plasma samples will then be sent for bioanalysis using a validated method.

### 11.2. Plasma PK Endpoint

The  $C_{trough}$  in plasma of ME3183 and its metabolite (CCI [REDACTED]) will be summarized descriptively by treatment group in the Tables, Figures and Listings (TFLs).

### 11.3. Presentation of Concentration Data

#### 11.3.1. Handling of Missing Data

Missing concentration data for all subjects who are administered study drug will be considered as non-informative missing and will not be imputed. No concentration estimates will be provided for missing sample values.

For individual plasma concentration vs. time curves, the following rules will apply:

- Concentration values below the limit of quantification (BLQ) of the corresponding analyte (ME3183 or CCI [REDACTED]) in samples will be treated as zero, with the exception of calculation of geometric mean and geometric coefficient of variation% (CV%), for which these assessments will be excluded.

#### 11.3.2. Listing and Presentation of Individual PK Data

The following presentations of individual PK concentrations will be produced:

- Listing of PK sampling times including nominal and actual time elapsed from dose with the deviation from the nominal time and measured concentrations of the drug.

Individual  $C_{trough}$  concentrations in linear scale for all subjects by treatment combined on one graph and plotted for each day.

### 11.4. PK Parameters Derivation

No PK parameters derivation is planned for ME3183 and its metabolite (CCI [REDACTED]) concentrations.

#### 11.4.1. PK Parameters Summarization

For summarization of PK data for ME3183 and its metabolite (CCI [REDACTED]), the following data handling measures will be employed:

- The mean/median value at a time point where 1 or more samples have BLQ values will be reported even if the mean/median value is BLQ.
- Zero mean or median values will be included in summary tables.
- SD will not be displayed if more than 30% of values are missing or BLQ.

This document is confidential.

- Tables of summary statistics for concentration-time data will be reported as per below table.

The following summary presentations of mean PK concentrations for ME3183 and its metabolite (CCI [REDACTED]) will be produced:

- Table of PK concentrations summarized by nominal time for each treatment separately.
- Mean  $C_{trough}$  profiles in linear scale for both treatments vs. nominal time.

Variable	Summarized with:
plasma concentration at each time point	n, number and % BLQ, arithmetic mean, SD, coefficient of variance (CV) %, Geometric mean and CV%, minimum, median and maximum

CV% = SD/mean in %.

%BLQ = 100 \* (total number of subjects who have BLQ values/total number of exposed subjects within treatment group, with a PK assessment at each time point).

